To collect data on fetal and neonatal outcomes, birth and maternal complications in case of pregnancies exposed to ella®.

To assess the nature and incidence of complications of pregnancy loss in pregnancies exposed to ella®.

Design

Prospective observational study.

Population

Pregnant women in the USA, who have been exposed to ella®:

- during the menstrual cycle in which the pregnancy started or
- at any time during pregnancy.

Women will be directly enrolled in the study using a website interface that will be accessible to Health Care Professionals (HCP) and women themselves.

Sample size

A sample size of 400 pregnancies with known outcome was chosen as it provides 80% power to detect a two-fold increase (Risk Ratio=2) for events with a proportion of 3% and a three-fold increase (RR=3) for events with a proportion of 1% (e.g., approximately equivalent to the total prevalence of congenital heart defects).

Data collection

Detailed clinical data on ella® exposure, pregnancy course and pregnancy outcomes, including fetal and neonatal outcomes, maternal pregnancy complications, medical history and use of other medications will be collected online using the study website.

Statistical analyses

The data collected in this study will be pooled with all reports of pregnancies collected by the Sponsor which include outcome information. Additional data sources include other clinical trials and Pharmacovigilance reporting. Pregnancy outcomes will be analyzed on the pooled dataset.

Baseline characteristics data of enrolled and completed cases will be described: age, pregnancy status at time of ella® exposure, dates of unprotected intercourse, last menstrual period, and ella® intake.

Each pregnancy outcome will be described as a proportion of pregnancies, with 95% exact confidence intervals.

Birth, maternal and pregnancy complications will be evaluated for each individual case, and the relationship with ella® exposure will be assessed according to the standard Pharmacovigilance process.

Proportions of adverse outcomes of ella®-exposed pregnancies will be compared with those from a suitable general reference population that would comprise essentially all non-exposed pregnancies, e.g. for congenital anomalies, population would be based on data from registries for congenital anomalies, notably members of the European Surveillance of Congenital Anomalies, EUROCAT.

Sponsor's pharmacovigilance responsibilities

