8 STUDY PROCEDURES AND SCHEDULE

8.1 Overview of safety data

Pregnancy information

Date of diagnosis, date of LMP, date and results of ultrasound (if applicable) and expected delivery date.

Exposure to ella®

Data on exposure to ella® include date of ella® intake and number of tablets taken, time from intercourse to ella® intake; pregnancy stage at ella® exposure, pregnancy status before ella® intake.

Outcomes

All outcomes and the data collected to assess them are:

- Live birth – gender, birth weight, gestational age, delivery method and Apgar scores will be collected in all cases. For healthy babies and those with congenital anomalies or other neonatal diagnosis, the study observation period will last until 4 months after delivery;
 - Congenital anomaly or other neonatal diagnosis – description of anomaly and possible causes will be additionally collected;
 - Neonatal death (from birth through to 28 completed days of age*) – age at death, possible etiology and result of autopsy if performed will be additionally collected.
- Pregnancy loss – gestational age, possible etiology of pregnancy loss and any complications (vaginal bleeding, need for curettage, infection) will be collected in all cases.
 - Spontaneous abortion (or early fetal death i.e. < 20 completed weeks of gestation*)
 - Ectopic pregnancy
 - Induced abortion (no medical reason – woman's elective choice, elective abortion with fetal defects, or maternal health complications)
 - Stillbirth:
 - Intermediate fetal death (more than 20 completed weeks of gestation but less than 28*)
 - Late fetal death (\geq 28 completed weeks of gestation*).

Maternal health complications of pregnancy

In all cases, relationship of the outcome observed with the exposure to ella® will be assessed by the HCP and according to the standard pharmacovigilance process.

* According to the WHO International Classification of Disease (ICD)

Prior and concomitant medications

Prior and concomitant medications will be collected in the HCP or women questionnaires. Collection period covers the pregnancy duration from LMP to the end of pregnancy.

Other

Maternal family history; recreational drug use (tobacco, alcohol, illicit drugs) and serological and prenatal tests.

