9 STATISTICAL PROCEDURES

9.1 Sample size justification

As described below, a sample size of 400 pregnancies with known outcomes was chosen as it provides 80% power to detect a two-fold increase (Risk Ratio=2) for events with a proportion of 3% and a three-fold increase (RR=3) for events with a proportion of 1% (e.g., approximately equivalent to the total prevalence of congenital heart defects) (refer to Annex 1).

Sample size and confidence interval calculations were done using Stata (version 11, Statacorp) and EpiInfo (CDC, Atlanta, GA) software programs.

Estimates for sample size requirements were performed with the goal of detecting a signal, if one exists, of an increase in the proportion of adverse pregnancy outcomes for pregnancies exposed to ella® compared to a given reference population. For these calculations, it is assumed that event rates / proportions would be comparable for an unexposed population and its corresponding source population, as by far most (essentially all) pregnancies in the source population would be unexposed to ella®.

Sample size calculations were performed assuming a type-I (alpha) error rate of 0.05, two-sided tests and a ratio of exposed to unexposed group of 1:10. Higher ratios (e.g., 1:6 or 1:4) would require somewhat higher sample sizes for the exposed group (detailed calculations are not shown) but the difference would be relatively small as the main determinant of study power will be the number of pregnancies exposed to ella®.

Pregnancies exposed to ella® will come from various population sources. In this context, stratified analyses for country-specific (or regional) outcomes may be helpful but would pose substantial limits as to the power for detecting the statistical significance of any observed differences.

Various sources of data may be found for large numbers of (essentially all) unexposed pregnancies for different adverse pregnancy outcomes (e.g. for congenital anomalies, population-based data from registries for congenital anomalies, notably members of the European Surveillance of Congenital Anomalies, EUROCAT).

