The term proportion is being used here as the measure of the frequency of adverse outcomes (e.g., preterm delivery / intrauterine growth restriction) and/or a specific adverse event (e.g., stillbirths, congenital anomalies). This may represent a cumulative incidence or in case of congenital anomalies the total or live birth prevalence of an anomaly (prevalence is the accepted term in the field of congenital anomalies to take into account early / unrecognized pregnancy loss, which precludes a true calculation of an incidence rate for congenital anomalies in the general population).

Table 1 (Annex 1) presents the sample size requirements for comparisons of proportions of adverse outcomes in pregnancies exposed to ella® versus those in the general population (essentially all unexposed). In summary, a sample size of approximately 50 and 100 pregnancies exposed to ella® can provide sufficient power to detect a two-fold increase [Risk Ratio (RR) = 2] in the risk of an adverse event with a baseline frequency of 20 (such as miscarriage) and 10%, respectively [such as intrauterine growth restriction as defined at birth (i.e. Small for Gestational Age)]; for a 50% increase (RR=1.5), the corresponding sample sizes would be approximately 160 and 375, respectively. A sample size of approximately 200 would provide a power of 80% to detect a two-fold increase for an adverse pregnancy event with a proportion of 5% in the general population (such as preterm birth). A sample size of approximately 400 would provide 80% power to detect a two-fold increase (RR=2) for events with a proportion of 3% and a three-fold increase (RR=3) for events with a proportion of 1% (e.g., approximately equivalent to the total prevalence of congenital heart defects ^{[1],[2],[3]}). For rarer events (e.g., those noted in Table 2 – Eurocat data) with a proportion of 0.1% (e.g., oro-facial clefts with a

prevalence of approximately 1 per 1000) or 0.05% (e.g., major specific congenital anomalies such as spina bifida which has a baseline total prevalence of about 4-5 per 10,000), sufficient power to detect even a ten-fold increase (RR=10) would require, respectively, almost 500 and 1000 pregnancies exposed to ella®; detection of a three-fold increase (RR=3) would require approximately 4000 pregnancies exposed to ella® and 40,000 unexposed pregnancies.

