Confidence intervals are also provided for proportions of adverse outcomes that may be obtained for a given number of pregnancies exposed to ella® (Table 3, Annex 1). These confidence intervals will be used to evaluate the precision of estimates for assessing the frequency of various adverse pregnancy outcomes in the pregnancies exposed to ella®.

In addition, for sample sizes of 50, 100, 400 and 1000, one-sided 97.5% binomial exact confidence intervals were calculated for the proportion of adverse outcomes assuming that zero adverse events are observed for a given sample. The upper bounds of these confidence intervals (the lower bound is fixed at zero) can be used as an approximate indication of what may be the highest event rates that would be missed because of a limited sample size. In particular, these confidence intervals can be used to assess to what extent rare outcomes (e.g., specific congenital anomalies) may be missed given the (highest) sample sizes that may be feasible to collect.

In summary, sample size calculations described above and presented in detail in Table 1 (Annex 1) show that for relatively frequent events, e.g., spontaneous abortions, or a composite index of different adverse outcomes (e.g., intrauterine growth retardation, preterm delivery and congenital anomalies) with a baseline proportion of 20% and 10%, sample sizes of 50 and 100, respectively, can provide sufficient power to detect a two-fold increase in the risk of adverse events associated with exposure to ella®. For events with a baseline proportion of 5 and 3% in the population, the corresponding sample sizes would be 200 and 400, respectively. For rare outcomes such as specific congenital anomalies (Table 2, Annex 1), only very high increases in the risk (Table 1, Annex 1) may be detectable given feasibility considerations.

Taking into account the above calculations and feasibility considerations, a sample size of 400 pregnancy outcomes was chosen for the study.

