9.2.2.2 Primary Objective Assessments

The primary objective of this observational study is to estimate the rates of occurrence of outcomes of pregnancies exposed to ella® in order to detect a possible signal of concern for adverse outcomes related to exposure to ella®.

Each pregnancy outcome will be described by proportions (cumulative incidence/prevalence) with exact 95% confidence interval.

For each pregnancy outcome, data from all sources (past and current clinical trials, registry, spontaneous pharmacovigilance reporting) will be used. Outcomes to be evaluated are defined as follows:

All Induced abortions (due to a medical/non-medical reason):

Proportion of normal-appearing pregnancies (with analysable ultrasound results) before induced abortion = number of normal-appearing pregnancies with ultrasound compatible with normal growth and development/ number of pregnancies with analysable ultrasound results.

Therapeutic abortion (medical indication)

Proportion of therapeutic abortions = number of therapeutic abortions / number of pregnancies

Birth outcomes

Proportion of live births = number of live births/ total number of births

Proportion of healthy babies = number of live births without any anomaly (healthy babies) / number of deliveries

Total live birth prevalence of congenital anomalies = number of live births with congenital anomalies / number of live births

Proportion of neonatal deaths = number of neonatal deaths / number of live births

Congenital anomalies:

Total prevalence of congenital anomalies = total number of congenital anomalies (terminations of pregnancy for fetal anomaly (TOPFA), stillbirths, live births with congenital anomalies / total number of births (live births + stillbirths)

Pregnancy loss outcomes

Proportion of spontaneous abortions (or spontaneous abortion cumulative incidence) = number of spontaneous abortions / number of pregnancies

Proportion of intermediate fetal deaths* = number of intermediate fetal deaths / number of pregnancies

Proportion of stillbirths (or stillbirth cumulative incidence) = number of stillbirths / number of pregnancies

* more than 20 completed weeks of gestation but less than 28, according to the WHO fetal death classification.

Proportion of ectopic pregnancies (or ectopic pregnancy cumulative incidence) = number of ectopic pregnancies / number of pregnancies with known outcomes reported

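### Spontaneous abortion and fetal death are divided by all pregnancies, including those ended electively; if elective abortion is more frequent or earlier than in the reference, the comparison is biased toward no signal.

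*Protocol*

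**What the plan says.** Protocol section 9.2.2.2 fixes the estimator: "Proportion of spontaneous abortions (or spontaneous abortion cumulative incidence) = number of spontaneous abortions / number of pregnancies". The lines for intermediate fetal death and stillbirth also divide by the number of pregnancies.

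Section 8.1 defines the event as "Spontaneous abortion (or early fetal death i.e. < 20 completed weeks of gestation". It lists induced abortion among the pregnancy losses, covering the woman's "elective choice, elective abortion with fetal defects, or maternal health complications". Electively ended pregnancies are therefore pregnancies with a known outcome and belong to the denominator. The protocol nowhere removes them, censors them at termination or uses a life table.

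The synopsis (Statistical analyses) states that proportions of adverse outcomes "will be compared with those from a suitable general reference population that would comprise essentially all non-exposed pregnancies", and section 9.2.2.4 tests the difference. Section 9.1 takes miscarriage as its example of the most frequent event, with a "baseline frequency of 20 (such as miscarriage) and 10%, respectively" for the next example, and says that about 50 exposed pregnancies give "sufficient power to detect a two-fold increase in the risk of adverse events associated with exposure to ella" at the 20% level. It plans for 400.

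**The concern.** A pregnancy ended electively at week 7 cannot miscarry in weeks 8 to 19, yet the formula counts it as a complete non-event. If the reference contains fewer such pregnancies, or later ones, the exposed proportion is pulled down relative to it for reasons unrelated to the drug. Women enrolled after treatment failure had taken ella to avoid pregnancy, so a higher share of elective abortion than in a general population is a reasonable expectation, although the protocol gives no figure.

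The direction matters. Section 9.2.2.2 gives signal detection as the purpose of these rates, and this bias hides a signal. It does not depend on late reporting: it remains even if every woman is followed from the start of pregnancy.

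**Working it through.** **Inputs from the protocol.** Reference miscarriage proportion 20%; risk ratio 2 (40%) or 1.5 (30%); exposed to unexposed 1:10; "assuming a type-I (alpha) error rate of 0.05, two-sided tests"; power 80%; 400 exposed pregnancies; spontaneous abortion means loss before 20 weeks.

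**Assumptions, not in the protocol.** Elective abortion share 30%, 50% or 70%, spread evenly in hazard over weeks 6 to 10; all women followed from week 5; weekly miscarriage hazard proportional to exp(−0.25 × (week − 5)); a reference with no elective abortions.

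**Step 1: the plan's own figure.** Table 1 gives 46 exposed for 20% against 40%.
- Pooled proportion = (0.40 + 10 × 0.20)/11 = 0.218.
- Uncorrected n = [1.96 × √(0.218 × 0.782 × 1.1) + 0.842 × √(0.24 + 0.16/10)]² / 0.20² = 40.6, rounded up to 41.
- With continuity correction: (40.6/4) × [1 + √(1 + 2.2/(40.6 × 0.20))]² = 46. The table is reproduced.

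**Step 2: the mechanism by hand.** Let e be the share who would terminate unless they miscarried first, and f the part of the miscarriage risk still ahead at termination. Crude proportion = true risk × (1 − e × f). With e = 50% and f = 0.5: 0.40 × 0.75 = 30%, ratio 1.5. With f = 1 (every termination before any miscarriage risk) it is 20%, ratio 1.0; that is the extreme case.

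**Step 3: weekly model.** Scale the miscarriage hazards so that 1 − ∏(1 − h) over weeks 5 to 19 equals 20% or 40%. Add an abortion hazard in weeks 6 to 10 that yields the stated share, and count miscarriages over all pregnancies.

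| Elective abortion | Crude, true 40% | Apparent ratio vs 20% | Power, 400 exposed | Crude, no effect | Abortions dropped, no effect |
|---|---|---|---|---|---|
| 30% | 33.7% | 1.69 | >99% | 17.1% | 24.4% |
| 50% | 28.9% | 1.45 | 98% | 15.0% | 29.9% |
| 70% | 23.2% | 1.16 | 34% | 12.5% | 41.7% |

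Power uses the uncorrected form. For 28.9%: difference 0.089; standard error 0.0213 under no difference and 0.0235 under the alternative; (0.089 − 1.96 × 0.0213)/0.0235 = 2.01, so 98%.

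**Step 4: a true ratio of 1.5.** At 50% abortion a true 30% appears as about 22%, ratio about 1.1. Power with 400 is about 20%, against 99% undiluted.

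**Step 5: sensitivity.**
- Order of events within a week: the crude values in the second column become 33–35%, 28–30% and 22–25%. Power with 400 is then 95% or more at 50% abortion, and roughly 15% to 68% at 70%.
- Fall of miscarriage hazard at 50% abortion: a decay of 0.1 per week gives a ratio of about 1.3 (power about 74%); 0.5 per week gives about 1.7.
- Reference carrying 20% elective abortion with the same timing: its crude value is about 18.1%, and the ratios become 33.7/18.1 = 1.86, 28.9/18.1 = 1.60 and 23.2/18.1 = 1.28.
- Equal share and timing in both groups: 33.7/17.1 = 1.97, 28.9/15.0 = 1.93, 23.2/12.5 = 1.86. In the one-step formula of Step 2, equal dilution cancels exactly.

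The last column of the table shows that deleting the abortions is no remedy. Women who miscarry before a planned termination stay in, so the estimate overshoots 20% with no effect at all.

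**The case against.** The crude proportion is a legitimate quantity. The primary objective is to describe how often each outcome occurs, and with termination as a competing event, cases over all pregnancies is a valid cumulative incidence. This stands. The fault lies in comparing it with a reference whose denominator may differ.

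The reference side is unknown. The protocol asks for a suitable reference, makes testing conditional on having one, and names EUROCAT only for congenital anomalies. It does not say whether terminations are in the denominator behind the 20%. This also stands: the sizes above hold only for the reference assumed. But nothing in the plan requires a matched reference either.

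Section 9.2.2 leaves details to the analysis plan, which is not at hand. That does not remove the point, because section 9.2.2.2 already fixes the formula.

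A reader might infer that the study cannot detect a doubling of miscarriage, or that it needs 164 exposed pregnancies (Table 1, ratio 1.5 at 20%) rather than 46. The documents do not support this: 400 are planned, well above both. A reader might also take the reference to be free of elective abortion, or treat a 70% share as a fact of this population. Neither is in the protocol.

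**Conclusion.** The point holds as a conditional bias. Followed as written, the plan understates miscarriage, intermediate fetal death and stillbirth relative to the reference whenever elective abortion is more frequent or earlier among exposed women; with equal share and timing the bias essentially disappears.

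For miscarriage, under the Step 3 assumptions, the main loss at 30% to 50% elective abortion is an understated effect size, since a doubling would still be detected with 400. Detection itself becomes unreliable near 70%, or when the true increase is about 50% rather than two-fold. The 70% power figure is the least stable, as the sensitivity checks show. No size was derived for intermediate fetal death or stillbirth, where only the mechanism is established.

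**What to change.** For the reference comparison, estimate spontaneous abortion and fetal death by gestational week with a life table. Let each pregnancy enter at its gestational age when it was reported, censor it at elective induced abortion, and use the pregnancies that have the needed dates. Delayed entry is necessary because reports are accepted at any time from diagnosis until the outcome is known (sections 3 and 8.4). Compare with a reference that handles terminations in the same way; a life-table estimate set against a crude 20% would create a new mismatch.

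Keep the crude proportion in section 9.2.2.2 as description. Show crude proportions with elective abortions in and out of the denominator as a sensitivity range.

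The cost is modest for this study's own cases, because date of last menstrual period and gestational age at loss are already collected (section 8.1). There are three drawbacks. The method assumes that the decision to abort is unrelated to miscarriage risk at that week. Intervals are somewhat wider. Pooled reports without dates, or reported only after the outcome, drop out of this estimate, so their number should be given.

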2 STUDY OBJECTIVES

2.1 Primary objective

[figure not shown]
The primary objective of this observational study is to assess the rates of occurrence of outcomes of pregnancies exposed to ella® (whether due to failure of the emergency contraception or inadvertent exposure during pregnancy). Data analyzed will come from this prospective observational study, other studies and pharmacovigilance reporting.

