4 SELECTION OF WOMEN

4.1 Number of women

As per rationale detailed in section 9.1, a total of 400 ella®-exposed pregnancies with known outcomes will be analysed.

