4.3 Inclusion criteria

Women meeting all the following criteria will be considered for admission to the study:

- Pregnant women in the USA, exposed to ella® during the menstrual cycle in which the pregnancy started (treatment failure) or at any time during pregnancy (inadvertent exposure during pregnancy)
- Written informed consent provided:
 - When the questionnaire is completed by the HCP, the ICF will be downloaded from the website and 2 print-out copies signed by the woman. One signed copy will be given to the woman for her records.
 - When completed by the woman, an electronic signature will be requested on the ICF module and the woman will be requested to save and/or print-out the ICF for her records.

5 INFORMATION ON ella® SUPPLY

HRA Pharma will not supply any medication. Women will be enrolled after having taken commercially available ella®.

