9.2.2.1 Descriptive analysis

Descriptive statistics (mean, standard deviation, 95% confidence interval for mean, minimum, median, maximum, and number of observations and missing cases) for quantitative variables, and proportions (cumulative incidence or prevalence) for categorical variables will be calculated with binomial or Poisson exact confidence intervals. The proportion of cases that are lost to follow-up will be described.

Baseline characteristics data of enrolled and completed cases will be described: age, pregnancy status at time of ella® exposure, time from unprotected intercourse to exposure in case of treatment failure, or time from LMP to exposure in case of inadvertent use as well as multiple ella® intakes since her LMP.

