These proportions (cumulative incidence) of adverse events and their 95% confidence intervals will be calculated for the overall sample as well as by country, in order to assess potential differences due to variations in clinical practice regarding the management of pregnancies and pregnancy complications. Results will also be presented by age.

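### Outcome proportions are broken down by country and age but not by exposure type, so a harm confined to the smaller exposure group would be diluted in the pooled figure

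*Protocol*

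**What the plan says.** Section 2.1 sets one primary objective over all exposed pregnancies, "whether due to failure of the emergency contraception or inadvertent exposure during pregnancy". Section 4.3 admits women "exposed to ella® during the menstrual cycle in which the pregnancy started (treatment failure) or at any time during pregnancy (inadvertent exposure during pregnancy". Section 4.1 sets the size for both kinds together: "a total of 400 ella®-exposed pregnancies with known outcomes will be analysed".

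Sections 8.1 and 8.2.1.2 collect the intake date, the stage of pregnancy at exposure and the pregnancy status before intake. In the analysis, section 9.2.2.1 uses this information to describe the cases at baseline: "time from unprotected intercourse to exposure in case of treatment failure, or time from LMP to exposure in case of inadvertent use".

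Section 9.2.1 pools all data sources. Section 9.2.2.2 then gives the primary proportions and their intervals for the whole sample and for each country, adding "Results will also be presented by age". Section 9.2.2.3 repeats the same breakdowns for the secondary proportions. No section crosses an outcome with exposure type or timing. The multivariable models in section 9.2.2.4 depend on a sufficiently large sample and name no covariates.

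**The concern.** Section 9.2.2.2 says that the rates are estimated in order to detect a signal of harm related to exposure. Country and age are not features of the exposure; its timing is. Two consequences follow from showing only the pooled figure.

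- **Dilution.** If an adverse effect occurs in one exposure group only, the other group pulls the pooled risk ratio towards 1. The smaller the affected group, the stronger the pull.
- **Mixed risk sets.** Section 9.2.2.2 divides spontaneous abortions by all pregnancies. A woman exposed in the conception cycle is at risk from the start. A woman exposed some weeks into pregnancy cannot have miscarried before that exposure. Pooling the two can lower the apparent loss proportion relative to a general reference rate, even if the drug has no effect.

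At stake is whether a timing-specific signal would be visible in the reported tables.

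**Working it through.** **Inputs from the protocol.** Section 9.1 calculates sample size "assuming a type-I (alpha) error rate of 0.05, two-sided tests and a ratio of exposed to unexposed group of 1:10". It says of 400 pregnancies that "it provides 80% power to detect a two-fold increase (Risk Ratio=2) for events with a proportion of 3" per cent, and likewise "a three-fold increase (RR=3) for events with a proportion of 1" per cent.

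**Step 1: reproduce the stated size.** With exposed risk p1, reference risk p0, d = p1 − p0, r = 10 and weighted mean p̄ = (p1 + r·p0)/(1 + r):

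n′ = [1.960·√((r+1)·p̄(1−p̄)) + 0.842·√(r·p1(1−p1) + p0(1−p0))]² / (r·d²)

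n = (n′/4)·[1 + √(1 + 2(r+1)/(n′·r·d))]²

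- 6% v 3%: n′ = 361.9, n = 397.7, so 398 as in Table 1 of Annex 1.
- 3% v 1%: n′ = 338.8, n = 391.9, so 392 as in Table 1.

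With 400 v 4,000, the power is 80.2% and 80.7%. Both figures require the increase to apply to all 400 pregnancies.

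**Step 2: dilution.** If a share f carries risk ratio RR and the rest carry 1, the pooled risk ratio is 1 + f(RR − 1). The protocol gives no f, so 10%, 20% and 30% are assumptions.

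**Step 3: power, pooled against stratum.** One-sample exact binomial test, upper tail 0.025, against a fixed 3%. The pooled test needs at least 20 events in 400 (12 expected; tail 0.020). The strata need 5 of 40, 7 of 80 and 9 of 120 (tails 0.007, 0.010 and 0.010).

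| Inadvertent share (n) | RR in that group | Pooled risk | Pooled RR | Pooled power | Stratum power |
|---|---|---|---|---|---|
| 10% (40) | 2 | 3.3% | 1.1 | 5% | 9% |
| 20% (80) | 2 | 3.6% | 1.2 | 9% | 20% |
| 30% (120) | 2 | 3.9% | 1.3 | 16% | 29% |
| 10% (40) | 3 | 3.6% | 1.2 | 9% | 29% |
| 20% (80) | 3 | 4.2% | 1.4 | 24% | 59% |
| 30% (120) | 3 | 4.8% | 1.6 | 46% | 76% |

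**Step 4: the reverse case.** If RR = 2 applies only to a group making up 90% (n = 360), the pooled RR is 1.9. Pooled power is 76% and stratum power 75%, so the split gains nothing.

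**Step 5: sensitivity to the test.** Using the protocol's two-group comparison with 4,000 reference pregnancies (continuity-corrected normal approximation), pooled against stratum power at shares of 10%, 20% and 30% is 4% v 17%, 9% v 29% and 16% v 40% at RR = 2. At RR = 3 it is 9% v 44%, 24% v 68% and 45% v 82%. The direction is the same. With only 1.2 events expected in 40 pregnancies at 3%, the exact figures are the safer guide.

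**Step 6: risk sets.** Without any drug effect, let q be the loss risk from conception and q′ the remaining risk at a later exposure, with q′ < q. The pooled proportion is (1 − f)q + f·q′, which is below q. This needs no assumed risk ratio. Its size depends on f and on the stage at exposure, and the protocol gives neither distribution.

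**Step 7: precision.** With zero events, the 97.5% one-sided upper limit is 1 − 0.025^(1/n): 0.9% at n = 400 (as in Table 3), 3.0% at 120, 4.5% at 80 and 8.8% at 40.

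**The case against.** Section 9.2.2 leaves the detail of the analyses to a statistical analysis plan, which is not at hand, and nothing in section 9.2.2.2 excludes further tables. That stands: the protocol does not forbid the split, and its absence from an unseen plan is not the point. But the protocol itself chose the breakdowns. It kept country although section 9.1 concedes that country-specific analyses would have little power, and it left out the variable that defines eligibility.

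A reader might infer that the pooled proportion fails to answer the primary objective. The wording does not support that. Section 2.1 asks for rates in exposed pregnancies of either kind, and the overall proportion answers it.

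A reader might also take the RR = 3 rows as the expected gain. At a 3% baseline, section 9.1 targets RR = 2, where stratum power is only 9% to 29%. The split would usually miss that harm too. For congenital anomalies the denominators are births, so real strata would be smaller still.

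Timing is not ignored elsewhere. Under sections 11 and 11.1 the data monitoring board reviews outcomes in batches of 50 with menstrual and intake dates at hand. For a handful of events, case review may tell as much as a wide interval. It does not, however, produce a rate by exposure type.

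Finally, section 8.4 allows reporting at any time from diagnosis to known outcome. Delayed enrolment therefore affects both groups, and splitting them does not remove that bias.

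**Conclusion.** The point holds as a cheap improvement to breakdowns that the protocol fixes poorly, not as an error or an internal contradiction. The pooled proportion is valid as an overall description, but it weakens any harm confined to the smaller exposure group and mixes risk sets for spontaneous abortion.

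Under the assumed shares of 10% to 30%, a 3% baseline and harm in the inadvertent group only, pooled power is 5% to 16% at RR = 2 and 9% to 46% at RR = 3. In the stratum it is 9% to 29% and 29% to 76%. These figures rest on an exposure mix that the protocol does not give and on an effect that differs by timing. If the harm lies in a 90% majority, there is no gain. The main benefit is an undiluted estimate; adequate power is not restored in these exact-test scenarios.

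**What to change.** Add to sections 9.2.2.2 and 9.2.2.3 that each proportion, with its exact 95% confidence interval, is also given separately for treatment failure and for exposure during pregnancy. Divide the latter by gestational age at exposure where numbers allow, and include a row for unknown timing. Label these results as descriptive estimation, not as powered tests.

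The cost is extra table columns from data the forms already collect, with no change to enrolment. The price in precision is wide intervals in the smaller stratum. Bias from delayed enrolment remains and needs separate handling.
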